### **2.3.2 Baseline, Changes from Baseline and Direction of Differences**

The latest measurement taken on or before day 1 prior to the first injection will be the baseline measurement. In addition, within each treatment cycle, “cycle baseline” is defined as the most recent evaluation prior to the current cycle’s treatment. Changes from baseline will be based on the day 1 baseline (rather than cycle baseline) unless otherwise stated.

Change from baseline will be calculated as followup minus baseline. The interpretation of a positive or negative change from baseline is specific to the outcome measure and will be discussed as needed. Treatment differences will be reported as BOTOX minus placebo and as BOTOX (higher total dose) minus BOTOX (lower total dose).

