### **2.3.5 Handling Drop-out or Missing Data**

For efficacy analyses of mITT population of the change from baseline in lower facial volume using VECTRA 3D images, MMPS, lower facial width, mandibular facial angle, CT masseter muscle volume, LFSC, and LFSQ, last observation carried forward (LOCF) will be used to impute missing values for each scheduled visit. Only missing data for visits up to day 180 of each treatment cycle will be imputed. Missing data for visits after day 180 of each cycle will not be imputed. If a subject exited the study before day 180 of a treatment cycle, visits after the study exit will not be imputed.

Missing baseline values for lower facial width, mandibular facial angle, CT masseter muscle volume, LFSC, and LFSQ will be imputed using the average of subjects with non-missing values. Missing values for change from baseline in lower facial volume using VECTRA 3D images at day 30 will be imputed using the average of subjects with non-missing values.

For angle measurements, the average degree from both sides of the face will be determined first; if the degree of angle is missing for 1 side of the face, then the angle for the subject will be based on the angle of the other side of the face. If a subject's average is a half-degree value, it will be rounded up to an integer (eg, 30.5 degree will be rounded up to 31 degrees).

For rating an individual's MMPS score, the average of the scores from both sides of the face will be determined first; if a score is missing for 1 side of the face, then the score for the subject will be based on the score of the other side of the face. If a subject's average is a half-grade value, it will be rounded up to an integer to remain consistent with the original scale (eg, 1.50 will be rounded up to 2).

When implemented, imputation of missing values will be performed only for subjects who receive a treatment in the pertinent treatment cycle. For example, only subjects receiving the second treatment will have values imputed in treatment cycle 2; subjects who discontinued from the study during the first treatment will not have any data imputed in treatment cycle 2.

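### When an angle is measured on both sides at one timepoint but on one side at the other, the change from baseline is off by half the left-right difference

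*SAP*

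**What the plan says.** SAP 2.3.5 fixes the order of steps: "For angle measurements, the average degree from both sides of the face will be determined first". It then adds that "if the degree of angle is missing for 1 side of the face, then the angle for the subject will be based" on the side that remains. An average that falls on a half degree is rounded up to a whole degree.

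SAP 2.3.2 then applies one general rule: "Change from baseline will be calculated as followup minus baseline". Baseline is the last value before the first injection, and changes refer to that baseline in both treatment cycles unless stated otherwise. Neither section says that the two terms of the subtraction must rest on the same side or sides.

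Two further rules in SAP 2.3.5 bear on the point. The mandibular facial angle is among the measures filled by LOCF up to day 180 of each cycle. A missing baseline angle is replaced by the mean of the subjects who have one, which is a subject-level value.

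**The concern.** A change score should compare like with like. Here a subject's angle can be a two-sided average at one timepoint and a single side at the other. Any natural difference between the two sides then enters the change, even if neither side has moved. The artefact depends on the subject's anatomy and on which side was lost, not on treatment.

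The same convention does little harm for the MMPS. Protocol 4.3 requires identical left and right grades at entry, so at baseline either side equals the average. No readable criterion requires equal angles.

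A one-sided follow-up value affects that visit and any later missed visit that LOCF fills from it. A one-sided baseline affects every two-sided visit in both cycles, because all changes use the day 1 baseline.

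**Working it through.** The plan gives no figure for the angle to reproduce. Its one design figure, 93% power (Protocol 7.5), is for lower facial volume. With 40 versus 10 subjects, effect size 1 and one-sided 0.10, a noncentral t with 48 df gives 0.936, so it reproduces. Nothing below touches it.

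**Inputs**
- L and R are the side angles, with 0 for baseline and 1 for follow-up.
- Subject angle: (L+R)/2 with both sides, or the single side (SAP 2.3.5).
- Change: follow-up minus baseline (SAP 2.3.2).
- Assumed, because the documents give none: the left-right difference, the share f of subjects with one side missing at exactly one timepoint, and a change SD of 3 degrees.

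**Step 1: one subject**
- Both sides at baseline, right only at follow-up: R1 - (L0+R0)/2 = (R1 - R0) + (R0 - L0)/2.
- Right only at baseline, both sides at follow-up: (L1+R1)/2 - R0 = (R1 - R0) - (R1 - L1)/2.

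In each case the result is the remaining side's own change, plus or minus half the left-right difference at the timepoint where both sides were measured.

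Take L = 30 and R = 36 with no true change, so the average is 33:
- right only at follow-up: 36 - 33 = +3
- left only at follow-up: 30 - 33 = -3
- right only at baseline: 33 - 36 = -3
- left only at baseline: 33 - 30 = +3
- same side at both timepoints: 36 - 36 = 0, or 30 - 30 = 0

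For assumed differences of 2, 4 and 6 degrees the artefact is 1, 2 and 3 degrees in size. If one side is available at baseline and only the opposite side at follow-up, the whole difference enters: 36 - 30 = +6.

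**Step 2: rounding**

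With 30 and 33 the average of 31.5 becomes 32. Right only at follow-up gives 33 - 32 = +1 rather than +1.5, and left only gives 30 - 32 = -2 rather than -1.5. The half-difference result therefore holds to within 0.5 degree.

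**Step 3: group level**

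If the lost side is random, the expected shift is 0 and the added variance is f × SD²/4, where SD is that of the left-right difference (taken as independent of the true change).
- f = 2%, SD = 2: 0.02 × 4/4 = 0.02, and √(9 + 0.02)/3 = 1.001, an increase of 0.1%.
- f = 10%, SD = 6: 0.10 × 36/4 = 0.90, and √(9 + 0.90)/3 = 1.049, an increase of 4.9%.

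If the same side is always lost and the mean difference is 2 degrees, the group mean shifts by f × 2/2, which is 0.02 to 0.10 degrees for f of 2% to 10%. The shift cancels in BOTOX minus placebo if it is the same in both arms.

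**The case against.** The strongest case against the point is that the situation may hardly arise. Protocol 1.2 takes the mandibular facial angle from 2D images projected from the VECTRA 3D models, so a failed capture or missed visit would plausibly remove both sides together. The documents give no rate of one-sided loss and no asymmetry. The rule is also the same in every arm, and the measure is neither primary nor secondary. Attachment 12.1.5 and much of the SAP text after section 5.3 are not visible, so a same-side rule there cannot be excluded.

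All of this stands as a limit on size. It does not remove the defect: the SAP provides for one-sided angles, and the value that its readable rules produce for such a subject is wrong by simple algebra.

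The rule is worded for angles in general, so it might also reach the CT flare and gonial angles in SAP 6.5. Those are listed left and right and may be summarised by side, so the documents do not settle it.

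**Conclusion.** The point holds as a small one. Under the readable text, a subject with both sides at one timepoint and one side at the other gets a change that is off by half the left-right difference at the two-sided timepoint, to within the rounding step. In the example that is 3 degrees in either direction with no true change.

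A reader might infer that facial asymmetry will be reported as a treatment effect. The documents do not support that. The sign depends on which side is lost, and a shift between arms needs one-sided missingness that is related to both arm and side, which nothing in the documents suggests. What remains is mainly noise in individual change scores for the mandibular facial angle. Its size rests entirely on assumed asymmetry and missingness. The primary analysis, the secondary analysis and the stated power are unaffected.

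**What to change.** Add one sentence to SAP 2.3.5: when an angle is missing on one side at baseline or at follow-up, the change from baseline is that of the side available at both timepoints, follow-up minus baseline on that side. If baseline and follow-up each have one side but not the same one, treat that visit's change as missing under the existing rules.

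Leave the averaging and half-degree rounding unchanged for subjects with both sides measured. Leave the subject-level imputation unchanged where the baseline angle is missing altogether.

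A broader repair, averaging the per-side changes for everyone, may look equivalent but is not. Take both sides measured, 30 and 33 at baseline and 30 and 32 at follow-up. The SAP gives 31 - 32 = -1, because 31.5 is rounded up to 32. Averaging the side changes gives (0 + (-1))/2 = -0.5. That repair would alter results for fully measured subjects; the same-side sentence does not.

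The cost is that sentence and a small programming change, with no new data. If unseen text already matches sides, a cross-reference from SAP 2.3.5 is enough. The sentence should also say whether it covers the CT angles.

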#### 1.2 Rationale for Efficacy Assessments

In the medical literature, various imaging methods have been used to assess effects of botulinum toxin on masseter muscle size and lower facial shape (refer to the Investigator's Brochure). Technologies used to measure quantitative changes in masseter muscle volume have included ultrasound, computed tomography (CT), and magnetic resonance imaging (MRI). Photographic technologies developed to provide 3-dimensional (3D) quantitative analysis of facial morphology include image subtraction technique, moire topography, liquid crystal scanning, light luminance scanning, laser scanning, stereo-lithography, and passive stereophotogrammetry (Adriaens, 2012; Kim et al, 2005; Tzou and Frey, 2011), which all measure change to the lower facial contour. Previous studies reported peak efficacy of botulinum toxin treatment of MMH at 3 months (Hong et al, 2005; Kim et al, 2003; Kim et al, 2007; Park et al, 2003), therefore, day 90 is the primary timepoint in the present study.

In the present study, the VECTRA M3 3D Stereophotogrammetry system

and CT imaging will be used to quantify the effect of BOTOX by lower facial volume (Attachment 12.1.2) and masseter muscle volume (Attachment 12.1.3), respectively. The VECTRA system has previously been validated for use in the facial region (de Menezes, 2010), and data from this study will be used to validate its use in the defined lower facial area encompassing the masseter muscle. In addition, the lower facial width (Attachment 12.1.4) and mandibular facial angle (Attachment 12.1.5) will

be calculated using 2-dimensional (2D) images projected from the VECTRA M3 3D image models.

Allergan developed the MMPS, a clinician's assessment tool for evaluation of masseter muscle prominence associated with MMH (see Attachment 12.1.1). The MMPS is to be used by trained clinicians to evaluate and grade the hypertrophy of the masseter muscle on the left and right sides of the face. The MMPS is a static measurement encompassing both visual and palpable examination of the masseter muscle both at rest and at jaw-clench state. The MMPS showed substantial inter- and intra-rater reliability in the nontreatment scale validation Study 191622-128, confirming its acceptability for use in the present study.

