## **6.5 CT Scan Safety Measures**

Using a standardized protocol, CT scans for each subject will be captured by a CT technologist at screening (baseline), treatment cycle 1 day 90, and the exit visit, and the 9 measures listed below will be assessed by a central reader.

For each of the quantitative measures, summary statistics will be presented for baseline, mean change from baseline, and percent change from baseline (sample size, mean, standard deviation, median, minimum, and maximum) by treatment regimen for all scheduled visits.

For each of the qualitative measures, the incidence of change from baseline will be summarized on a per-subject basis. Interpretation of change from baseline will be provided by the central reader in comments.

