#### *Quantitative Safety Measures*

1. bigonial width (mm)
2. cortical thickness under the insertion point of the masseter muscle at the mandibular ramus (mm) (left and right)
3. mandibular flare angle (degrees; left and right)
4. gonial angle (degrees; left and right)

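### SAP 2.3.5 rounds a half-degree left-right average of the mandibular facial angle up to a whole degree, which gives away a little precision for no stated reason

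*SAP*

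**What the plan says.** SAP 2.3.5 (Handling Drop-out or Missing Data) sets the derivation: "For angle measurements, the average degree from both sides of the face will be determined first". If one side is missing, the other side stands in for the subject. The section then says that if a subject's "average is a half-degree value, it will be rounded up to an integer", and its example takes 30.5 to 31. It gives no reason.

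The next paragraph applies the same rule to the MMPS and does give one: "If a subject's average is a half-grade value, it will be rounded up to an integer to remain consistent with the original scale".

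The only angle named in SAP 2.3.5 is the mandibular facial angle. It appears in the list of efficacy measures to which LOCF applies, and again in the list of measures whose missing baselines are filled with a mean. Protocol 1.2 says that this angle will "be calculated using 2-dimensional (2D) images projected from the VECTRA M3 3D image models". SAP 2.3.2 defines change as follow-up minus baseline.

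The readable text gives no recording precision, expected change or SD for the angle. The measurement method is referred to Protocol Attachment 12.1.5, which is not in the public text, and part of SAP section 5 is blacked out.

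**The concern.** The average of two sides is already available without rounding. For an ordinal grade, moving a half-grade average to a whole grade keeps the result on the scale. Degrees have no such set of grades, and the MMPS reason is not claimed for them.

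Change is a difference of two visits, so rounding can enter twice. It then adds random error that the analysis need not carry. What is at stake is precision on one supporting efficacy measure. Lower facial volume (primary) is not an angle, and the MMPS (secondary) has its own rule.

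**Working it through.** **Figures in the plan.** There is no figure for angles to reproduce. The only power figure, 93% in Protocol 7.5 (40 against 10, effect size 1, one-sided 0.10), concerns lower facial volume. It reproduces at 93.6% (noncentral t, 48 df) and 93.9% (normal approximation). Nothing below depends on it.

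**Inputs.** From SAP 2.3.5: a mean of two sides, with exact half degrees rounded up. From SAP 2.3.2: follow-up minus baseline. Assumed: the precision of each side's reading, and an SD of change of 1 to 5 degrees.

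**1. Error in one value.** Let p be the share of averages that end in exactly .5. The rounding error is +0.5 with probability p and 0 otherwise, so its mean is 0.5p and its variance is 0.25p(1-p). With whole-degree sides the average ends in .5 whenever the two readings sum to an odd number, so p is about 0.5. The mean shift is then 0.25 degree.

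**2. Error in a change score.** Treat the two visits' rounding as independent.
- The error is +0.5 with probability 0.5 x 0.5 = 1/4, -0.5 with probability 1/4, and 0 with probability 1/2.
- The mean error is 0.25 - 0.25 = 0.
- The added variance is 2 x 0.25 x 0.5 x 0.5 = 0.125, and the added SD is the square root of 0.125, or 0.35 degree.

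**3. Loss of precision.** The inflation is 0.125 divided by the squared SD of change. The power column is an illustration with assumed inputs: 40 against 40, two-sided 0.05, a true difference of 0.65 SD, and 82.8% power without rounding.

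| Assumed SD of change (degrees) | Added variance | Power with rounding |
|---|---|---|
| 1 | 12.5% | 78.3% |
| 2 | 3.1% | 81.7% |
| 3 | 1.4% | 82.3% |
| 5 | 0.5% | 82.6% |

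**4. Simulation check.** With 1,000,000 subjects per scenario and whole-degree sides, the share of half-degree averages was 0.50, the shift in level 0.25 degree, the added SD 0.353 degree and the largest error 0.5 degree. Mean change with and without rounding agreed to within 0.001 degree, for true changes of 0 and -1 degree. At a nominal SD of 1 the simulated inflation was about 9.3%, not 12.5%. The reason is that the simulated readings carried their own reading error, so the unrounded SD was 1.15: 0.125 / 1.33 = 9.4%.

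**5. One side missing at one visit only.** That visit uses a single whole-degree reading and is never rounded, so the 0.25 degree shift at the other visit does not cancel. The expected error is +0.25 degree if baseline is the incomplete visit and -0.25 degree if follow-up is. If 5% of subjects were affected, all in the same direction (assumption), a group mean would move by 0.05 x 0.25 = 0.0125 degree.

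**6. Sides read to decimals.** With readings to 0.1 degree, averages move in steps of 0.05, so about 1 in 20 ends in exactly .5 (p = 0.05). The added variance is 2 x 0.25 x 0.05 x 0.95 = 0.024, SD 0.15 degree. The rule also stops preserving order. Sides of 30.3 and 30.7 average 30.5 and become 31, while sides of 30.4 and 30.8 average 30.6 and stay there. Both sides are larger by 0.1, yet the recorded value is smaller by 0.4.

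**The case against.** The best defence is that this hardly matters. The rule is prespecified, deterministic and the same in every arm. It leaves mean change essentially unbiased and touches neither key endpoint. Unless the SD of change is near 1 degree, the loss in the example is about one point of power or less. All of that stands.

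A second defence is that whole-degree readings may each be off by up to half a degree, so a whole-degree average claims no more than was recorded. That justifies rounding for display. It does not justify rounding before analysis, which adds a further error to the one already there.

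A third is that text not visible here may give the precision or a reason for whole degrees. That is possible. It is why the size is stated as conditional.

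Two stronger readings are tempting. A reader might infer that the rule also governs the CT gonial and flare angles, because SAP 2.3 says its conventions apply to all analyses. The documents do not establish this. SAP 2.3.5 opens with mITT efficacy analyses and names only the mandibular facial angle. SAP 6.5 lists the CT angles by side and gives them their own summaries: "For each of the quantitative measures, summary statistics will be presented for baseline, mean change from baseline, and percent change from baseline". A related worry, that a one-sided bone change could be hidden, concerns averaging and not rounding, and it depends on the same unsupported reading.

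A reader might also infer that every change score is disturbed, or that angle changes are known to be small. Under the whole-degree assumption only about half of change scores are altered, and the readable text gives no expected angle change.

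**Conclusion.** The point holds as a minor one, limited to the mandibular facial angle. The rule has no stated reason and does no useful work at either precision: with whole-degree sides it adds noise, and with decimal sides it acts rarely and can reverse order.

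The size rests on assumptions: whole-degree readings (suggested by the rule addressing only half degrees, but not stated), independent rounding at the two visits, and an SD of change that the documents do not supply. On those terms the added SD is 0.35 degree, noticeable near an SD of change of 1 degree and negligible from about 3 degrees upward. It costs precision and does not favour an arm. The exception, one side missing at one visit only, is confined to the affected subjects; its frequency is not given, and nothing in the text suggests that it differs by arm.

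**What to change.** In SAP 2.3.5, delete the half-degree rounding sentence for angles. State that the unrounded left-right average is analysed and that any rounding is for display only. Keep the rule that uses the other side when one is missing, and keep the MMPS rounding rule unchanged.

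The cost is a short SAP amendment and a small change to one derived variable. No new data are needed, since the side-level readings already exist.

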### **2.3.6 Descriptive Statistics**

Data will be summarized with descriptive statistics and/or response frequencies. Descriptive statistics for continuous variables include the sample size (N), mean (Mean), standard deviation (SD), median (Median), minimum (Min), and maximum (Max). Descriptive statistics for categorical variables include the sample size (N) and frequency (counts and percentages).

### **2.3.7 Significance Level**

The level of significance used for all statistical tests will be 0.05, 2-sided, unless stated otherwise.

### **2.3.8 Confidence Intervals**

For dichotomous variables, 2-sided 95% confidence intervals for proportions will be calculated based on the normal distribution approximation, unless otherwise stated.

### **2.3.9 Dictionaries**

The Medical Dictionary for Regulatory Activities (MedDRA) will be used to code adverse events, medical history, and medications. MedDRA primary system organ class (SOC), MedDRA high level term (HLT), together with the drug record number and base preferred drug name from the enhanced version of World Health Organization Drug Dictionary (WHO DDE) will be used to classify all medications (ie, prior or concomitant) recorded in the study. Base preferred name is the WHO DDE drug preferred name assigned to the 11-digit code of drug record number+01+001.

### **2.3.10 Units**

Metric system units will be used; degrees Celsius for temperature, kilograms (kg) for body weight, and centimeters (cm) for height.

## **3. Disposition and Exit Status**

### **3.1 Screening Log Data**

The subject counts and percentage for the reasons for screening failure will be displayed for the following categories: inclusion criteria, exclusion criteria, and total. In addition, subjects who fail to pass screening will be compared to randomized subjects with descriptive statistics for age, sex, and race. No statistical tests are planned to compare groups.

### **3.2 Disposition and Exit Status**

The analysis will be performed using the mITT, and Safety population for the entire study and by treatment cycle.

The disposition of study subjects will consist of a summary of the number of subjects enrolled and available in the mITT, and Safety analysis populations by treatment regimen and overall.

The summary will be further enhanced by tabulating the number of subjects remaining in the respective treatment groups of each treatment cycle.

Tabulation of the number and percentage of subjects in each exit status category (ie, adverse event, pregnancy, lost to follow-up, personal reasons, protocol violations and other) will be provided for each treatment regimen of each treatment cycle. Discontinued subjects will be listed along with the corresponding reason(s) for early withdrawal from the study.

